# 11.2 Clinical Laboratory Evaluations

In this study, blood will be sent for analysis to a central laboratory for all cycles Day 1 visits, in addition to collecting the local lab results. The focus of the report will be based on these central laboratory results for all summary tables. Listings will be presented with both the central and local lab results. In addition, since glucose is a laboratory variable of interest the analyses around glucose will include both the central laboratory results and the local laboratory results.

Clinical laboratory evaluations include the continuous variables for hematology, serum chemistry, and urinalysis. Laboratory values will be presented in Standard International units. The baseline laboratory value will be defined as the last value prior to or on the day of the first dose of oral CO-1686. The on-treatment period will be defined as the day after the first dose of

oral CO-1686 to 28 days after the last dose of CO-1686. Laboratory values collected during the on-treatment period will be included in the summary tables. The laboratory values collected after the on-treatment period will only be presented in the data listings.

The summary of laboratory data will include descriptive statistics (N, mean, standard deviation, minimum, median, and maximum) of the maximum, minimum, and last value during the treatment period by dose group and study phase. Summaries using descriptive statistics of the change from baseline to the maximum, minimum, and last value during the on-treatment period will also be given by dose group and study phase. Separate listings will be produced for clinically significant laboratory abnormalities (i.e., those that meet Grade 3 or 4 criteria according to CTCAE).

The time to first Glucose value > 13.875 mmol/L will also be summarized. The time to first occurrence of a glucose value > 13.875 mmol/L will be calculated as 1+ the number of days from study drug start date to the first date of the glucose value > 13.875 mmol/L. Patients who do not have an observed glucose value > 13.875 mmol/L will be censored on the date of their last visit or data cutoff date for ongoing subjects.

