CO-1686 causes hyperglycemia in some patients secondary to inhibition of the insulin-like growth factor 1 receptor (IGF-1R) and insulin receptor (IR) kinases by a metabolite. Therefore, some patients will require addition of a glucose lowering medication and patients with pre-existing diabetes may require more frequent monitoring and/or adjustments of diabetic medication. Clinical experience with CO-1686 suggests hyperglycemia generally occurs within the first 3 weeks of treatment, leading to the need for more intensive glucose monitoring during the first several weeks of the study. In Phase 1/2 clinical trial experience, increased nausea and vomiting, and decreased appetite, diarrhea, muscle cramps and fatigue have been reported in patients with hyperglycemia. Such patients must be closely monitored including assessment of fasting glucose levels and early initiation of anti-hyperglycemic therapy. As CO-1686-induced hyperglycemia is mediated through insulin resistance, agents that suppress glucose synthesis (metformin), increase sensitivity to insulin (glitazones) or increase glucose excretion (sodium-glucose cotransporter 2 [SGLT2] inhibitors) are expected to be more effective than those that increase plasma insulin (sulphonylureas or exogenous insulin). Metformin has been

used most frequently in CO-1686 clinical studies and is, therefore, recommended as the initial agent to manage hyperglycemia in patients with normal renal function. In addition, preliminary data from the ongoing Study CO-1686-008 suggest that starting metformin at the same time CO-1686 therapy is initiated may prevent the development of CO-1686-induced hyperglycemia. For all patients, irrespective of whether they are receiving metformin prophylactically or therapeutically, glucose monitoring should be conducted according to the following schedule:

- Fasting glucose will be measured at the following visits: Screening, C1D1, C1D4 (± 1 day), C1D8 (± 1 day), C1D15 (± 1 day), C2D1, C2D15 (± 1 day), C3D1, C4D1, C5D1, CND1... and End-of-Treatment Visit.

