9.2.1 Cycle 1 Day 1 (C1D1)

Patients will be required to take their first dose at the clinic with 8 oz (240 mL) of water and with a meal or within 30 minutes after a meal.

To be performed *before* dosing:

- Physical examination
- Weight
- ECOG performance status
- Vital signs (blood pressure, pulse, and temperature)
- Concomitant medications and procedures
- Fasting serum chemistry (including fasting glucose)
- Hematology (including reticulocyte count)
- Blood sampling for biomarker/EGFR mutational testing and exploratory research
- Blood sampling for CYP testing (requires optional consent)
- AE monitoring
- CO-1686 tablets will be dispensed to the patient; patient diary will be provided to the patient
- 12-lead ECG (in triplicate, 10-sec tracings > 2 min apart) 5-10 minutes prior to dosing
- QoL Questionnaires (EORTC QLQ-C30, EORTC QLQ-LC13, and the DLQI)

To be performed *after* dosing:

- AE assessment
- Concomitant medications and procedures

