Appendix C, Table 2. Hyperglycemia Lab-shift by Acetylator Status

	Overall (N = 635)		
	Slow (n = 300)	Intermediate (n = 259)	Rapid (n = 76)
Subjects with any post-baseline glucose values > 250 mg/dL	121 (40%)	65 (25%)	17 (22%)
Subjects with 2 or more post-baseline glucose values > 250 mg/dL	51 (17%)	36 (14%)	7 (9%)
Subjects with any post-baseline glucose values > 500 mg/dL	11 (4%)	7 (3%)	1 (1%)
Subjects with 2 or more post-baseline glucose values > 500 mg/dL	3 (1%)	0 (0.0)	0 (0.0)

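### Time to first glucose > 13.875 mmol/L has no at-risk condition, so a patient already above the limit at baseline can count as an early first occurrence

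*SAP*

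**What the plan says.** The last paragraph of SAP 11.2 defines the event time as "1+ the number of days from study drug start date to the first date of the glucose value > 13.875 mmol/L". For everyone else, "Patients who do not have an observed glucose value > 13.875 mmol/L will be censored on the date of their last visit", or at the data cutoff if the patient is ongoing. The analysis set is the safety population (SAP 11), meaning every patient with at least one dose. The glucose analyses use both central and local results.

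Earlier in the same section, three general rules for laboratory data are set:

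- Baseline: "The baseline laboratory value will be defined as the last value prior to or on the day of the first dose of oral CO-1686".
- Window: "The on-treatment period will be defined as the day after the first dose of" oral CO-1686, running to 28 days after the last dose.
- Use: "Laboratory values collected during the on-treatment period will be included in the summary tables".

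The glucose paragraph neither repeats nor cites these rules, and it gives no instruction for a patient whose baseline is already above 13.875 mmol/L.

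Such a patient can be enrolled. The laboratory limits in Protocol 6.2 cover marrow, liver, kidney and electrolytes, but not glucose or HbA1c. Diabetes is not among the exclusions in Protocol 6.3. Protocol 7.4 expects diabetic patients: "patients with pre-existing diabetes may require more frequent monitoring and/or adjustments of diabetic medication". A footnote to Figure 7-1 confines its guidance to patients who are not diabetic at study start. Fasting glucose is measured at Screening, before dosing on C1D1, and next at C1D4 ± 1 day.

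**The concern.** A time-to-first-event summary describes onset only if the patients in the risk set can still have the event for the first time. Here a patient who enters above the limit is in the risk set from the start. If that patient stays above it, the first qualifying measurement is recorded as a first occurrence although nothing new has happened. Prevalent and new elevations are then mixed in one curve.

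Hyperglycemia is described in the protocol synopsis as the most common toxicity, and SAP 11.2 singles out glucose as a variable of interest. Protocol 7.4 places onset mainly in the first 3 weeks of treatment and bases the intensity of early monitoring on that. Misplaced events would fall in just that period. SAP 2.2 says these data support the safety conclusions of the initial MAA and NDA submissions.

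**Working it through.** **Threshold.** Protocol 7.4 equates 250 mg/dL with 13.87 mmol/L, and the SAP uses 13.875. Check: 250 × 0.0555 = 13.875. The two are the same limit, so Appendix C, Table 2 of the protocol (250 mg/dL) can be used for scale.

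**Event times under each reading.** The formula is time = 1 + (event date − first-dose date).

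| Value above the limit | Days from first dose | Literal reading | With the on-treatment window |
|---|---|---|---|
| Screening, 28 days before | −28 | 1 − 28 = −27 | not used |
| Day before dosing | −1 | 1 − 1 = 0 | not used |
| C1D1, before dosing | 0 | 1 + 0 = 1 | not used (baseline) |
| C1D4 ± 1 day | 2 to 4 | already counted | 3 to 5 |

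On the literal reading the definition can return zero or negative times, so it is incomplete without a window. With the window, pre-dose values drop out, but the patient stays in the risk set and becomes an event at time 3 to 5 days if glucose is still above the limit. The window settles which values count. It does not settle who is at risk.

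**Size.** Inputs:

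- N = 125 (SAP 2.2, approximate).
- Share ever above the limit after baseline: (121 + 65 + 17)/(300 + 259 + 76) = 203/635 = 32.0% (Appendix C, Table 2). This is pooled over 500 to 1000 mg BID and is borrowed here as an assumption.
- Share above the limit at baseline, b: not given in the documents. Assumed range 0 to 5%.
- Every patient above the limit at baseline is taken to exceed it again on treatment, which gives the largest overstatement.

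Expected events are 0.32 × 125 = 40. Among patients at risk, the proportion is (40 − 125b)/(125 − 125b).

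| b | Patients above limit at baseline | Share of the 40 events | All dosed | At risk only | Difference (points) |
|---|---|---|---|---|---|
| 0% | 0 | 0% | 32.0% | 32.0% | 0 |
| 1% | 1.25 | 3% | 32.0% | 38.75/123.75 = 31.3% | 0.7 |
| 2% | 2.5 | 6% | 32.0% | 37.5/122.5 = 30.6% | 1.4 |
| 3% | 3.75 | 9% | 32.0% | 36.25/121.25 = 29.9% | 2.1 |
| 5% | 6.25 | 16% | 32.0% | 33.75/118.75 = 28.4% | 3.6 |

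**Literal reading at b = 5%.** Suppose none of the 6.25 patients exceeds the limit again. Their pre-dose values still count, giving (40 + 6.25)/125 = 37.0%, against 40/118.75 = 33.7% among patients at risk. The difference is 3.3 points, within the 3.6 bound.

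**Start of the curve.** Each affected patient adds 1/125 = 0.8 points. At b = 5% the early step is at most 6.25/125 = 5.0 points, at time 3 to 5 days with the window and at Day 1 or earlier without it.

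**The case against.** The strongest reply is that SAP 11.2 already supplies the window. It makes the C1D1 value baseline, starts the on-treatment period the next day and sends on-treatment values to the summary tables. The event formula also counts forward from drug start. On that reading no pre-dose value can be an event. This is a fair reading and probably the intended one. However, the glucose paragraph does not say so, and SAP 11.3 uses a different window for vital signs, starting at the first dose. More importantly, the window leaves the persistent elevation at C1D4 untouched.

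A second reply is that a threshold summary in all dosed patients is a legitimate description, and that baseline context appears elsewhere: baseline laboratory grades (SAP 6.2), medical history (SAP 6.3) and change from baseline (SAP 11.2). That stands for a simple count of patients ever above the limit. It does not rescue a time to first occurrence.

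A reader might infer more than this from the text, in three ways that the documents do not support:

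- That pre-existing hyperglycemia will be reported as immediate CO-1686 toxicity. Day 1 and negative times arise only on the literal reading, and SAP 11.2 makes no causal attribution. Treatment-related events are tabulated separately under SAP 11.1.
- That the bias is known to be material. No baseline prevalence is given. Glucose is measured fasting and Protocol 6.3 excludes serious or unstable systemic disorders incompatible with the study, so the number affected may be zero.
- That Appendix C, Table 2 is a precedent for excluding patients by baseline glucose. Its row "Subjects with any post-baseline glucose values > 250 mg/dL" restricts the values to post-baseline ones, but the denominators are the full acetylator groups. It supports the window only.

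**Conclusion.** The point holds in limited form. SAP 11.2 states no at-risk condition for this analysis and leaves its window implicit, so under either reading a patient who enters above 13.875 mmol/L can be counted as a very early first occurrence.

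The overstatement of the overall proportion is at most 0 to about 3.6 percentage points. That rests on 125 patients, a 32% event share borrowed from pooled data, an assumed 0 to 5% above the limit at baseline, and persistence in all of them. These are upper bounds: with the window, a patient whose elevation does not persist is not an event at all. If nobody enters above the limit, nothing changes. Any effect is concentrated in the first days of the curve. The analysis is descriptive, with no test or decision rule attached, and the primary ORR analysis is unaffected.

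**What to change.** In SAP 11.2, add to the paragraph on time to first glucose > 13.875 mmol/L that:

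1. only on-treatment values, dated after the first-dose date, count as events;
2. the summary is restricted to patients with baseline glucose at or below 13.875 mmol/L;
3. the number of dosed patients already above the limit at baseline is reported on a separate line.

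The first item makes explicit a rule that the section already contains. The second is new, and the third keeps the omitted patients visible. No new data are needed. The cost is a slightly smaller denominator: at the top of the assumed range, about 6 of 125 patients.

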#### 11.3 Vital Signs

The on-treatment period will be defined as the time from the first dose of study drug to 28 days after the last dose of study drug. Vital sign measurements collected during the on-treatment period will be included in the summary tables.

The summary of vital sign data will include descriptive statistics (N, mean, standard deviation, minimum, median, third quartile and maximum) of the maximum, minimum and last value during the on-treatment period. Summaries using descriptive statistics (N, mean, standard deviation, minimum, median and maximum) of the change from baseline to the maximum, minimum, and last value during the on-treatment period will also be given.

Graphs of the mean values over time may also be provided.

# 11.4 12-Lead Electrocardiograms

The electocardiograms (ECGs) will be centrally read for this study. The ECG measurements (an average of the triplicate measurements) will be used for the statistical analysis and all data presentations. QT intervals will be corrected for heart rate (QTc) using standard correction factors of both Fridericia's (QTcF) and Bazett's (QTcB).

Electrocardiogram (ECG) intervals will be stratified into categories indicative of potential clinical significance. Each patient's maximum QT and QTc intervals from the pretreatment visit and treatment period visits will be classified as ≤450 msec, >450 to ≤480 msec, >480 to ≤500 msec, and >500 msec. For each patient's maximum change from the pretreatment ECG visit for QT and QTc, intervals will be classified into <30 msec, ≥30 to <60 msec, and ≥60 msec. Patients will also be classified according to the CTCAE grade 3 criteria of at least 2 on treatment QTc values >500ms. The number and percentage of patients in each classified category will be presented.

Descriptive statistics may be used to summarize other ECG parameters of PR, QRS, QT, and RR interval, and the corresponding changes from pretreatment ECG visit at each time point.

# 12 SUMMARY OF CHANGES FROM PROTOCOL SPECIFIED ANALYSES

Due to the accelerated approval strategy with the NDA submission, the data presented in the NDA will be a subset of the overall study with patients enrolled up to the 31st of December with a visit data cutoff of 29 April 2015. Hence, due to the ongoing nature of the data in this trial the following analyses will not be performed at the time of the NDA version but will be performed when the study is completed:

#### Secondary endpoints:

- Progression-Free Survival as determined by the Investigator
- Progression-Free Survival as determined by the Independent Radiology Review
- Overall survival
- Disease control rate will be summarized for both the independent radiology assessment and the investigator assessment
- To assess quality of life (QoL) by patient-reported outcomes (PRO) following CO-1686 treatment

#### **Exploratory Objectives**

- To evaluate clinical benefit of continued CO-1686 treatment following disease progression
- To evaluate concordance of mutant EGFR detection between tissue and plasma and assess CO-1686 mediated alterations in mutant EGFR levels over time using ctDNA obtained from plasma
- To explore tissue and blood-based biomarkers that may be predictive of response or primary resistance to CO-1686 and investigate mechanisms of acquired resistance in the tissue and blood of patients who experience clinical progression during treatment with CO-1686.
